cardiopulmonary bypass strategy based on blood gases and operative documents.

Inclusion Criteria:

• Age less than 30 days of age at time of surgery with need for cardiopulmonary bypass with

cardioplegic arrest (with or without deep hypothermic circulatory arrest)

• Diagnosis with cyanosis at baseline (pre-operative PaO2 of less than 50mmHG) due to:

o Complete admixture lesion (example: hypoplastic left heart syndrome, total anomalous

pulmonary venous return, truncus arteriosus, pulmonary atresia with VSD)

o Transposition physiology (example: D-Transposition of the great arteries or Double

outlet right ventricle with subpulmonary VSD)

o Right-to-left shunt (example: Tetralogy of Fallot, double outlet right ventricle with

suboaortic VSD and pulmonary stenosis)

Exclusion Criteria:

• Corrected gestation at time of surgery less than 37 weeks

• Prior cardiac arrest

• Current or prior history of ECMO support

• Current or prior history of needing renal replacement therapy with dialysis

• Prior cardiac surgery requiring cardiopulmonary bypass

• Diagnosis of Ebstein's Anomaly

• Known genetic syndrome other than Trisomy 21 or DiGeorge Syndrome

ProtocolVersion: 1.4 Date: 03122021

7

Subject Availability:

Based on historical data, the number of patients that fit the inclusion criteria would be about 40-50 patients

per year in this single center study. A sample size of 21 patients per treatment group (42 total patients) will

be enrolled. With a 50-67% consent rate, the study duration will be approximately 24 months.

Trial Enrollment and Randomization:

Infants will be randomized into two groups:

1. Normoxia Group (with controlled re-oxygenation):

a. Goal PaO2 on cardiopulmonary bypass of 60-100 mm Hg using lower FiO2 (blended

sweep gas) via oxygenator

b. Post-bypass, goal of PaO2 < 100 mm Hg by anesthesia and in ICU via oxygen titration via

mechanical ventilator for 24 hours post-op.

2. Standard of Care Group: Current standard of care

Randomization will be performed in random permuted block sizes of 2 or 4 and stratified by "Stage I

Palliation" (Norwood arch reconstruction with shunt placement [Right ventricle-to-pulmonary artery shunt,

modified Blalock-Taussig shunt, or central aortopulmonary shunt]) in each treatment group. Patients

undergoing Stage I palliation are known to have higher rates of complications and mortality at baseline and

therefore the stratification will be done to control for this in the randomization.

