Study Protocol:

Please see Figure 2 for a summary of the study protocol.

1. Preoperative:

Patients that meet the defined inclusion and exclusion criteria will be identified and the families will be

8

approached for consent prior to the scheduled surgery.

Patients that are enrolled in the study will have the following pre-operative studies:

ProtocolVersion: 1.4

Date: 03122021

• Head ultrasound (not currently standard of care but will be used to evaluate for any brain injury

in each group)

• Renal function and liver function panel (within 24 hours prior to surgery)

2. Operating Room:

Patients will be brought to the operating room in a standard fashion. Anesthesia will induce general

anesthesia per protocol and secure an airway (if needed) and place invasive lines. Patients will have labs

drawn (baseline biomarkers of oxidative stress, troponin level, and Redox potential) and an arterial blood

gas.

All patients will have a median sternotomy and be cannulated onto cardiopulmonary bypass via standard

procedures at the discretion of the surgery team.

3. Initiation of Cardiopulmonary Bypass:

The cardiopulmonary bypass circuits will be set up and primed per standard institutional protocols.

"Normoxia" Group: Prior to cannulation, a blood gas will be drawn from the cardiopulmonary bypass

circuit and correlated to the CDI (in-line PaO2 monitor). The FiO2 of the oxygenator will then be titrated

to achieve a PaO₂ of the circuit and CDI of 60-100 mm Hg. After cannulation, frequent blood gases will

be checked per protocol and correlated with the CDI to maintain a PaO₂ of 60-100 mm Hg.

"Standard of Care" Group: After cannulation, frequent blood gases will be checked per protocol on bypass

and correlated with the CDI to maintain a PaO₂ of 200-300 per standard practice.

4. Weaning of Cardiopulmonary Bypass:

At the end of re-warming, a blood sample will be obtained for appropriate studies.

"Normoxia" Group: As cardiopulmonary bypass is being weaned, anesthesia will initiate mechanical

ventilation with an FiO2 of 50% or less (unless clinically necessary) to achieve oxygen saturation and PaO2

9

goals that fit within the expected range for the patient's physiology:

1. Single ventricle patients (PaO₂:35-45 and oxygen saturation 75%-85%)

2. Two ventricle patients (PaO₂: 60-100 and oxygen saturation >92%)

ProtocolVersion: 1.4

. . .

Measures of oxygen delivery such as NIRS monitoring, mixed venous oxygen saturations, and

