Specific Aim 1: The primary outcome for this aim will be systemic oxidative stress based on thiobarbituric acid reactive substances (TBARS), a measurement of lipid peroxidation, assessed at three separate time points in the first 24 hours after surgery. An analysis of co-variance will be used incorporating all available data to model the outcome with an adjustment for pre-operative baseline (although we anticipate no differences in baseline values by treatment arm due to randomization). The model will compare the mean values (and 95% confidence intervals) between the two groups at each time-point. In this model, we will assume missing data are missing at random, i.e., missing values may depend on observed but not unobserved data. Analysis will be performed on the basis of the intent-to-treat principle and will include an interim analysis after 24 patients are enrolled. In secondary analyses, we will use propensity scores to

account for any characteristics that were not balanced by treatment arm after randomization. We plan to

analyze other biomarkers of oxidative stress and organ injury using analogous analysis of variance models.

Specific Aim 2: To evaluate safety, we will assess the rate of observed adverse events between groups using

Chi-square test or Fisher's exact test as appropriate. Safety will also closely be monitored on a routine basis

by the Data Safety and Monitoring Board (DSMB). .

Specific Aim 3: To investigate optimal endpoints in the study of the clinical impact of normoxia. We will

assess clinical endpoints that may be reflective of a reduction in oxidative stress, including post-operative

length of stay, days alive and out of the intensive care unit (ICU) at 30 days after surgery, a composite

outcome of major adverse events as described above, and a global rank score. For all endpoints, data on

distribution within our study population and between the two groups will be calculated to understand effect

sizes and aid in planning subsequent studies.

1. Post-operative length of stay: Calculated as number of days in the hospital after surgery. May be an

attractive outcome as it can incorporate many of the morbidities that would be influenced by strategies to

reduce oxidative stress as most would lead to prolonged length of stay. The disadvantages are that it does

not incorporate mortality, and may be influenced by other center care processes and practices.

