a. Incidence of arrhythmias requiring medical therapy

13

ŀ

- b. VIS score on admission, 2, 6, and 24 hours post-operatively
- c. Measurement of arteriovenous saturation difference:
 - Regional venous saturation measurements (NIRS), which are routinely collected in all patients (measurements will be recorded at 2, 6 and 24 hours after surgery)
 - ii. Pulse oximetry measurements and arterial oxygen saturation (via arterial blood gas) at 2, 6, and 24 hours after surgery
- d. Lactic acid production (highest and lowest value in 12-hour increments in the first 48 hours after surgery). Arterial blood gases are routinely obtained in the post-operative period
- e. Need for stress dose hydrocortisone in the post-operative setting
- f. Biomarkers: troponin release, vascular injury (ANGPT2) and inflammatory balance (IL-6, IL-10)

4. Kidneys:

- a. % above dry-weight daily for the first 5 post-operative days (Dry weight will be defined as dosing weight which will likely be the birth weight of the infant)
- b. Days to dry weight
- c. Serum creatinine levels (comparison of pre-op, daily trends in the first 3 days including identification of peak level)
- d. Biomarkers: NGAL (urine)

5. Oxidative stress:

- a. Whole blood redox potential
- b. Biomarkers (protein carbonyls, total antioxidant capacity (TAC), and 8-isoprostanes)

6. GI:

a. Liver function tests and intestinal fatty acid binding protein (I-FABP (pre-operatively, 24, 48, and 72 hours post-operatively)

b. Time to goal feeds

Table 3: Schedule of Evaluations

^{***} Can be run with already collected samples per SOC

Test	Pre-op (within 24hrs prior to surgery)	Baseline (in OR prior to bypass)	End Rewarming	2 hour post	6 hour post	24 hour post	Morning of POD 1	Morning of POD 2	Morning of POD3	General Post-Op for 48 hours	1 month Post- op
Blood **	0 mL	2.75 mL	2.25 mL	2.75 mL	2.75 mL	2.75 mL	0 mL	0 mL	0 mL		
Renal Function Panel	X SOC						X SOC	X SOC	X SOC		
Liver Function Panel ***	X R						X R	X R	X R		
TBARS		X R	X R	X R	X R	X R					
Protein Carbonyl		X R	X R	X R	X R	X R					
8-isoprostane		X R	X R	X R	X R	X R					
Total Antioxidant Capacity		X R	X R	X R	X R	X R					
Redox Potential		X R	X R	X R	X R	X R					
i-FABP		X R		X R	X R	X R					
Troponin		X R		X R	X R	X R					
GFAP		X R	X R			X R					
Tau		X R		X R	X R	X R					
ANGPT-2		X R		X R	X R	X R					
IL-6		X R		X R	X R	X R					
II-10		X R		X R	X R	X R					
Urine		***		***							
Urine: NGAL		X R		X R							
Neuroimaging and Testing											

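### The plan does not say whether the 12 other biomarkers are adjusted for their own pre-bypass baseline, and no model carries the Stage I randomization stratum

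*Combined protocol and SAP*

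**What the plan says.** Under Outcomes and Analysis, Specific Aim 1, the primary marker TBARS has a defined model: "An analysis of co-variance will be used incorporating all available data to model the outcome with an adjustment for pre-operative baseline". The same paragraph goes on: "The model will compare the mean values (and 95% confidence intervals) between the two groups at each time-point". It ends with the other markers, for which the plan is to "analyze other biomarkers of oxidative stress and organ injury using analogous analysis of variance models". Nothing further is said about covariates for them.

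Table 3 (Schedule of Evaluations) marks a research sample for every one of these markers in the column that begins "Baseline (in OR prior to bypass". The text under Study Protocol, 2. Operating Room is shorter. It says labs are "drawn (baseline biomarkers of oxidative stress, troponin level, and Redox potential) and an arterial blood" gas.

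Under Trial Enrollment and Randomization, allocation is stratified by Stage I palliation because those infants have more complications and higher mortality. The stratum does not appear again in the analysis section.

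**The concern.** One paragraph uses two method names. Analysis of covariance, with the covariate spelled out, is used for TBARS. Analysis of variance, which in ordinary usage has no continuous covariate, is used for everything else. Hypothesis 1b and the rest of Hypothesis 1a rest on the second name.

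Two things are at stake. If the literal reading were followed, intervals would be wider than they need be for any marker whose baseline predicts its later value, and part of any chance baseline difference would enter the estimate. And because the choice is not fixed, adjusted or unadjusted results could be chosen for 12 markers after the data are seen, in a trial that is not blinded.

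The missing stratum is a related gap. When randomization is stratified on a strong prognostic factor and the model leaves it out, the standard error tends to be too large.

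**Working it through.** **1. Is a baseline available for each marker?** Table 3, baseline column, apart from TBARS: protein carbonyl, 8-isoprostane, total antioxidant capacity, redox potential, i-FABP, troponin, GFAP, Tau, ANGPT-2, IL-6, IL-10 and urine NGAL. That is 12 of 12.

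**2. What do the two sentences fix?**

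| | TBARS | Other 12 markers |
|---|---|---|
| Method named | Analysis of covariance | Analysis of variance, *analogous* |
| Own baseline as covariate | Stated | Neither stated nor excluded |
| Stage I stratum | Not stated | Not stated |

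**3. Do the time points carry over?** Not for all. TBARS has 2, 6 and 24 hour samples after surgery. In Table 3, NGAL has one sample after baseline (2 hours), and GFAP has end of rewarming and 24 hours.

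**4. The plan's own figure.** The plan states: "A sample size of 21 patients per treatment group (42 total patients) will" be enrolled. 2 × 21 = 42 checks. No alpha, power, effect size or SD is given, so there is no power or precision figure to reproduce.

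**5. What the baseline term could be worth.** Assumptions not in the documents: true difference 0.6 SD, two-sided 0.05 (suggested by the planned 95% intervals), no missing data, one post-operative time point, and a baseline to follow-up correlation ρ from 0 to 0.7.

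- Unadjusted: noncentrality 0.6 × √(21/2) = 1.944, 40 df, critical t 2.021. Power is 47.5%.
- Adjusted: variance factor V = (1 − ρ²) × (1 + 1/38). The second term is the expected cost of estimating one covariate, with 38 = 42 − 4. Noncentrality is 1.944/√V, with 39 df and critical t 2.023.

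| ρ | 1 − ρ² | V | Noncentrality | Power, cost included | Power, cost ignored |
|---|---|---|---|---|---|
| 0 | 1.00 | 1.026 | 1.919 | 46.5% | 47% |
| 0.1 | 0.99 | 1.016 | 1.929 | 46.9% | 48% |
| 0.2 | 0.96 | 0.985 | 1.959 | 48.0% | 49% |
| 0.3 | 0.91 | 0.934 | 2.012 | 50.1% | 51% |
| 0.5 | 0.75 | 0.770 | 2.216 | 58.0% | 59% |
| 0.7 | 0.51 | 0.523 | 2.687 | 74.6% | 76% |

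V falls below 1 when ρ² > 1/39, that is, when ρ exceeds about 0.16. The largest loss from adjusting is 47.5 − 46.5 = 1.0 percentage point, at ρ = 0.

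**6. Chance imbalance.** The standard error of a baseline difference is √(2/21) = 0.309 SD. Without adjustment a fraction ρ of it reaches the follow-up comparison. A one-standard-error imbalance therefore shifts the estimate by 0.309 × ρ: 0.03 SD at ρ = 0.1, 0.15 SD at 0.5 and 0.22 SD at 0.7.

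The Stage I term is not in these figures, because the documents give nothing from which to size it. Stratified blocks keep it near balance between arms, so it costs little beyond one degree of freedom.

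**The case against.** The strongest reply is that the plan describes only one biomarker model before the disputed phrase, and that model is baseline-adjusted. *Analogous* most naturally points back to it, with analysis of variance used loosely as a family name. On that reading no precision is lost. This stands, and it limits the point to an ambiguity. A reader might infer that the plan drops the baseline and wastes samples already drawn. The documents do not support that: they never say that the baseline is left out, just as they never say that it is kept.

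Second, the plan foresees secondary propensity-score analyses for characteristics left unbalanced after randomization. That could pick up some imbalance, but it depends on what is observed and does not fix the covariates of the main comparison.

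Third, the plan itself expects balance: "although we anticipate no differences in baseline values by treatment arm due to randomization". That is true on average, but in a sample of this size the baseline term serves mainly precision.

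Fourth, the size of any gain is unknown and could be nil for markers with low correlation. This also stands.

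A reader might further infer from the short list in the Operating Room text that the other baselines will not be drawn. That goes too far. The list does not exclude other samples, the outcomes section refers to Table 3 for the biomarkers, and Table 3 budgets 2.75 mL at baseline, the same as at 2, 6 and 24 hours.

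**Conclusion.** The point holds as a gap in specification. Baseline adjustment is explicit for TBARS and unstated for the 12 other markers, while the Stage I stratum is named in no model. If *analogous* already carries the baseline over, that part of the edit only confirms intent; the stratum would still be new.

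Under the literal reading, and only under the assumptions above, the power forgone ranges from nothing (correlation up to about 0.1) to about 27 percentage points (74.6 − 47.5, at 0.7). The documents do not allow a choice within that range, so no single figure should be quoted as the loss. The markers are secondary or exploratory in a single-center pilot, so the consequence is modest. The edit is still worth making because it costs almost nothing.

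**What to change.** Replace the sentence on the other biomarkers with wording to this effect: each is analysed by analysis of covariance, with its own Table 3 baseline value and the Stage I stratum as covariates, at the time points after baseline that Table 3 gives for that marker (NGAL at 2 hours only; GFAP at end of rewarming and 24 hours). Add the Stage I stratum to the TBARS model as well. That model does not contain it now, so asking for the same model as TBARS would not be enough.

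Editorial alignment:

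- Bring the baseline list in the Operating Room text into line with Table 3.
- Reconcile the i-FABP times. The secondary outcomes list, which pairs it with liver function tests, gives pre-operative, 24, 48 and 72 hours; Table 3 gives baseline, 2, 6 and 24 hours.
- Reconcile the Post-Operative Course text, which has neurologic and renal markers at 2, 6 and 24 hours, with the narrower Table 3 schedule for GFAP and NGAL.

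The cost is a few sentences, with no samples beyond those in Table 3. The statistical price of the baseline term is at most about one percentage point of power in the illustration. The wording should be fixed before any comparison by arm is run, including the interim analysis planned after 24 patients.

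### Randomisation is stratified by Stage I palliation because it predicts complications and death, but the Aim 2 safety test and the Aim 3 effect sizes do not use the stratum

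*Combined protocol and SAP*

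**What the plan says.** Trial Enrollment and Randomization sets the design: "Randomization will be performed in random permuted block sizes of 2 or 4 and stratified by" Stage I palliation, with "A sample size of 21 patients per treatment group (42 total patients) will" be enrolled. The reason given is that these infants start at higher risk, and the protocol concludes: "therefore the stratification will be done to control for this in the randomization".

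Under Outcomes and Analysis, Specific Aim 2 says "we will assess the rate of observed adverse events between groups using" a "Chi-square test or Fisher's exact test as appropriate". Specific Aim 3 covers length of stay, days alive and out of the ICU, the composite of major adverse events and the global rank score. For these, data on "distribution within our study population and between the two groups will be calculated to understand effect" sizes and to plan later studies.

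The stratum appears in no analysis. The Aim 1 covariance model names only the pre-operative baseline. The secondary propensity scores, also in the Aim 1 paragraph, are for characteristics left unbalanced after randomisation, and a factor balanced by design would not trigger them.

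**The concern.** The outcomes that the protocol links to Stage I palliation, complications and mortality, are those compared in Aims 2 and 3: death, cardiac arrest, mechanical support, seizures, dialysis, and the endpoints built from them. Blocking within strata takes the difference between Stage I and other infants out of the arm comparison. An unstratified test still counts that difference as random variation, so it rejects less often than its nominal level and gives up some power.

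Two uses of the results are affected. Aim 2 is the only formal between-arm safety comparison, and its hypothesis is that events are similar or lower with normoxia. A conservative test makes an excess somewhat easier to miss. Aim 3 is meant to inform the next trial. A standard deviation pooled over a high-risk and a lower-risk group overstates the error variance that a stratified successor would face.

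**Working it through.** **Inputs from the protocol.** 21 infants per arm; permuted blocks of 2 or 4 within two strata; direction of the stratum effect only (Stage I higher).

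**Assumed, because the documents do not give them.** Two-sided 5% level, the number of Stage I infants per arm, and all event rates. Exact 1:1 balance within each stratum is also assumed; an incomplete last block could disturb this slightly. The protocol gives no power figure for Aims 2 or 3, so there is nothing to reproduce first.

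**Risk difference and its standard error.** Take 10 Stage I and 11 other infants per arm, with rates rising from 40%/10% (Stage I/other) to 75%/35%.

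- Control rate: (10×0.40 + 11×0.10)/21 = 0.2429. Normoxia rate: (10×0.75 + 11×0.35)/21 = 0.5405. Crude difference: 0.2976.
- Stratum-weighted difference: (10/21)×0.35 + (11/21)×0.25 = 0.2976. The estimate is the same, so omitting the stratum causes no bias here.
- Unstratified SE: √[(0.2429×0.7571 + 0.5405×0.4595)/21] = 0.1435.
- Stratified SE: √{[10×(0.40×0.60 + 0.75×0.25) + 11×(0.10×0.90 + 0.35×0.65)]/21²} = √(7.7675/441) = 0.1327.
- Ratio: 0.1435/0.1327 = 1.081, so the unstratified SE is about 8% larger.

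**Rejection rates.** All possible tables were enumerated exactly and weighted by their binomial probabilities. The entries are percentages rejecting at two-sided 5%.

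| Stage I/other per arm | Control rates | Normoxia rates | Chi-square | CMH | Fisher | Exact stratified |
|---|---|---|---|---|---|---|
| 10/11, no effect | 40/10 | 40/10 | 3.9 | 4.8 | 1.6 | 1.9 |
| 10/11 | 40/10 | 75/35 | 51.4 | 57.9 | 35.6 | 44.3 |
| 7/14, moderate stratum | 30/10 | odds ratio 4 | 45.1 | 46.8 | 30.2 | 33.7 |
| 7/14, weak stratum | 30/20 | odds ratio 4 | 55.6 | 54.2 | 40.6 | 42.7 |
| 10/11, very strong stratum | 50/5 | odds ratio 8 | 53.9 | 72.1 | 37.1 | 59.0 |
| 7/14, sparse | 15/5 | 30/10 | 11.6 | 12.1 | 5.5 | 5.0 |
| 10/11, sparse | 15/5 | 40/15 | 30.0 | 30.8 | 19.2 | 18.6 |
| 10/11, sparse | 10/3 | 30/10 | 23.8 | 24.1 | 13.3 | 11.5 |

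Chi-square to CMH changes power by 57.9 - 51.4 = +6.5 points in the second row, 54.2 - 55.6 = -1.4 with the weak stratum, and 72.1 - 53.9 = +18.2 with the very strong one. In the sparse rows the gain is 0.3 to 0.8 points, and the exact stratified test has slightly less power than Fisher's.

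**Continuous Aim 3 endpoints.** If Stage I explains a share R² of the variance, any unadjusted standard error is too large by the factor 1/√(1 - R²): 1.054 at R² = 0.10, 1.118 at 0.20 and 1.195 at 0.30. These R² values are assumptions.

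**The case against.** Several points on the other side stand.

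- **No interval is planned.** A reader might infer that the plan's error bars are too wide. Aim 2 names only a test and Aim 3 only distributions and effect sizes; confidence intervals are mentioned only for Aim 1. The standard-error results above describe what would follow if an unstratified error were attached. They also hold for risk and mean differences only. On the log-odds-ratio scale the stratified standard error is larger, though the estimate moves further from zero.
- **The protocol supports only a direction.** It says Stage I rates are higher, not by how much. With a weak stratum the gain disappears or reverses slightly.
- **Sparse events.** A reader might infer that stratifying helps every safety comparison. For single rare events CMH adds under one point, and an exact stratified test is marginally worse than the planned Fisher test.
- **Limited consequence.** A reader might infer that the plan hides harm. A non-significant result is not made a safety criterion, the DSMB reviews safety four times a year, and the Background leaves power for clinical outcomes to a larger multicentre trial. The difficulty in reading results as similar comes mainly from having no margin, which stratifying does not cure.
- **Aim 3 is descriptive.** Its wording does not exclude summaries by stratum, so part of this point asks for more detail and does not identify an error.

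None of this is a reason to leave out a prognostic factor that the trial already records and randomises on.

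**Conclusion.** The omission is real: a factor chosen because it predicts the clinical outcomes is used in the randomisation and in no analysis. If it is as prognostic as the protocol says, the unstratified test of the any-event composite is conservative. That is a loss of efficiency, with no bias in the risk difference and no inflation of type I error.

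The size cannot be fixed from the documents. Under the assumed rates and strata, chi-square to CMH gives about -1 to +18 points of power, about +6 in the central case, and about 0 to 1 for sparse single events. Part of the gap between Fisher's test and the others is Fisher's own discreteness, not the missing stratum. Power for harm remains low at 42 infants whichever test is used.

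A reader might extend the point to the Aim 1 model, which also omits the stratum. The protocol ties Stage I to complications and mortality, not to TBARS or the other biomarkers, so the documents do not support the same conclusion there. This is a cheap improvement to Aims 2 and 3, not a flaw that invalidates them.

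**What to change.** **Aim 2.** Compare the any-major-adverse-event composite with a CMH test stratified by Stage I palliation as randomised, and report the Mantel-Haenszel risk difference with a 95% interval. For sparse individual events keep Fisher's exact test and show the counts by stratum; an exact stratified test has no power advantage there.

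**Aim 3.** Report stratum-adjusted contrasts with 95% intervals: the Mantel-Haenszel difference for the composite, and a model with a Stage I term or a van Elteren test for length of stay, days alive and out of the ICU, and the global rank score. Where only the test is used, add an adjusted estimate so that an interval can be given. Tabulate within-stratum event rates and standard deviations beside the overall ones for planning the next trial.

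**Cost.** A few sentences of analysis text, best written before any comparison by arm, including the interim analysis after 24 patients. The stratum is already recorded, so no new data or patients are needed. The downside is that if Stage I proves only weakly prognostic, power for the composite can fall by about 1 point.
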